4.4. Ethics approval

This study will start following the approval of the institutional review board. All patients will be asked to read and sign an informed consent prior to their final recruitment to the study.

4.5. Population

We will offer this option to patients at the general clinic sites, orthopedic clinics, and general medical and rehabilitation practices of the Montefiore Medical Group and Departments of Orthopedics and Rehabilitation Medicine Practices, who would normally be referred for physical therapy for their knee pain.

Inclusion Criteria:

- Patients suffering from symptomatic knee OA (uni/bi lateral) for at least six months, fulfilling the ACR clinical criteria for OA of the knee, and having radiographically assessed OA of the knee according to the Kellgren and Lawrence scale.
- Patients with VAS pain score of ≥ 3 cm (measured at baseline).
- Males and females between the ages of 40-75.
- $17 < \text{BMI} < 40$
- Ambulatory and active patients that can participate in a rehabilitation program that includes daily walking
- Stable medical regimen (no recent pain medication changes within a month)
- Able to walk at least 50 meters
- Able to understand, read and sign the informed consent form
- English or Spanish speaking

Exclusion Criteria:

- Patients suffering from acute septic arthritis.
- Patients suffering from inflammatory joint disease such as rheumatoid arthritis.
- Patients who received a viscosupplementation/corticosteroid injection within 3 months of the study.
- Patients with diagnosis of avascular necrosis of the knee.
- Patients with diagnosis of neuromuscular disease.

- Patients with more than 3 falls in the last 12 months, OR any fall with an injury in the last 12 months.
- Patients exhibiting a lack of physical or mental ability to perform or comply with the study procedure.
- Patients with a history of pathological osteoporotic fracture
- Patients with referred pain in the knees from back or hip joint symptoms.
- Patients with severe back pain, ≥ 4 cm in visual analogue scale or radiating leg pain
- Patients with generalized body pain (both upper and lower extremities, such as fibromyalgia)
- No major surgery to the affected limb and contralateral limb (e.g. no joint replacements or surgical fracture repair)
- No major cardiovascular comorbidities (able to enroll in an active exercise program)
- Patient started on lipid lowering medication in last 3 months
- Any change in blood pressure medications
- No recent physical therapy (no more recent than 6 months) on the affected limb
- No active heart disease (ischemia or heart failure admissions within 6 months) and no active COPD (exacerbation within 6 months)
- No active malignancies
- Patient with neurological gait pattern [2]
- Patient requiring assistive device for gait analysis

4.6. Sample size

Our target recruitment is 147 individuals randomly assigned to one of two groups; traditional physical therapy or AposTherapy, on a 1:2 ratio. A sample size of 147 patients will yield 80% power to detect an expected difference on the WOMAC pain scale, with components measured on VAS scales from 0 to 10 and a summary score standardized to also range from 0 to 10, of 1.5 at a 2-sided alpha of 0.05. The difference corresponds to a

[figure not shown]
clinically meaningful moderate effect size of 0.4 standard deviation units assuming a typical standard deviation of 2.65. Anticipating an attrition rate of 10%, we aim at recruiting 162 patients for the trial (54 patients will be assigned to traditional physical therapy and 108 patients will be assigned to AposTherapy)

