Total number of patients	
One-hundred and forty-seven (147) individuals will be randomly assigned to one of two groups; traditional physical therapy or AposTherapy on a 1:2 ratio (49:98).
 
A sample size of 147 will yield 80% power to detect an expected difference on the WOMAC pain scale, with components measured on VAS scales from 0 to 10 and a summary score standardized to also range from 0 to 10, of 1.5 at a 2-sided alpha of 0.05. The difference corresponds to a clinically meaningful moderate effect size of 0.4 standard deviation units assuming a typical standard deviation of 2.65. Anticipating an attrition rate of 10%, we aim at recruiting 162 patients for the trial.

Study groups	
Patients will be randomly assigned to one of the following groups:
 
 • Patients with knee OA treated with AposTherapy • Patients with knee OA treated with traditional physical therapy
Assessment time points	
Patients will be enrolled in the study and have clinical evaluations at the following time points:
 
 • Pre-treatment • 4 weeks following treatment initiation

- 8 weeks following treatment initiation
- 12 weeks following treatment initiation
- 24 weeks following treatment initiation
- 52 weeks following treatment initiation

**The effect of AposTherapy on pain and function in Knee Osteoarthritis (OA) population. A
randomized controlled trial**

1. Background

AposTherapy is a home-based exercise program utilizing footwear that causes exercise with normal daily activity that may significantly improve function in patients with knee pain in general, and specifically knee osteoarthritis (OA). Capitalizing on the reported excellent adherence and clinical benefit of Apos Therapy in patients with significant lower limb arthritis, we propose to evaluate this as a conservative treatment that may supplant/supplement traditional pain medications and physical therapy in knee OA population. [3-6]

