4.9. Outcome measures

Primary study outcome:

- Western Ontario and McMaster Universities (WOMAC) pain scale at one year.
- WOMAC function scale at one year

Secondary study outcome: at: Pre-treatment, 4 weeks, 8 weeks, 12 weeks, 24 weeks, 52 weeks.

- WOMAC pain and function subscale
- PROMIS Pain Interference and Physical Function
- Costs: Assessment of total utilization and cost from resource utilization monitored via the CMO
- MOS item of the Short Form (SF)-36
- Spatio-temporal gait assessment including gait velocity, step length, single limb support and limb symmetry measured by Zeno Walkway ®
- 6-min walk test
- Blood pressure and resting heart rate

- Treatment adherence: Measured via attendance at sessions of therapy (conventional therapy), hours of use of AposTherapy (Patient to have step counter)
- Overall activity and sleep patterns (both arms (via FitBit Charge HR (<http://www.fitbit.com/chargehr#i.f9n1ye1ehxd30p>) motion sensor worn for one week after each evaluation session, mailed back via prepaid mailer at the end of the week.)

5. Statistical analysis

All demographic data will be reported as mean standard deviations and average. Data from primary and secondary outcome measures will be checked for skewness using Fisher-Pearson coefficient of skewness. ANOVA or Kuskal-Wallis test will be applied depending on normality of data. All statistical analysis will be conducted using IBM SPSS Statistics Ver.24.

6. Benefits

- Participants will all have physical therapy for their knee
- AposTherapy involves fewer visits to the physical therapy center thus allowing individuals more time at home and lower transportation costs
- AposTherapy is done at home and more convenient
- AposTherapy will be provided for free for participants.

7. Risks

- Muscle soreness associated with exercise
- Minimal fall risk with use of new footwear device and exercise

8. Subject Reimbursement

Participants will be reimbursed a total of \$40 at each assessment point (pre-treatment, at 4 weeks, 8 weeks, 12 weeks, 24 weeks and 52 weeks after entry into the study). Participants will

receive \$95 reimbursement for their time at the completion of the study after return of all devices and materials. This will apply to all arms of the study.

Study schedule:

Study Periods	Screening	1	2	3	4	5	6	7
Visit		1	2	3	4	5	6	7
Time (week)	-2	0	4	8	12	24	52	
Patient Information and Informed Consent	X							
Demographics	X							
Medical History	X							

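### The sample-size statement equates 1.5 points with 0.4 SD at an SD of 2.65, but that is 0.57 SD; power for 1.5 points is about 90%, not 80%

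*Combined protocol and SAP*

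**What the plan says.** Section 4.6 (Sample size) states that "A sample size of 147 patients will yield 80% power to detect an expected difference on the WOMAC pain scale", on a score running from 0 to 10, and puts the difference and test level as "of 1.5 at a 2-sided alpha of 0.05". It then describes the same difference as a "clinically meaningful moderate effect size of 0.4 standard deviation units assuming a typical standard deviation of 2.65". The synopsis row on the total number of patients makes the same statement ("of 1.5 at a 2-sided alpha of 0.05. The difference corresponds to a clinically meaningful moderate effect size of 0.4 standard deviation units") and gives the 1:2 split as 49:98.

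On numbers, section 4.6 opens with "Our target recruitment is 147 individuals randomly assigned to one of two groups". It then allows for dropout ("Anticipating an attrition rate of 10%, we aim at recruiting 162 patients for the trial") and gives the split of the larger figure: "54 patients will be assigned to traditional physical therapy and 108 patients will be assigned to AposTherapy".

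On the analysis, section 5 says only that "ANOVA or Kuskal-Wallis test will be applied depending on normality of data". It names no baseline covariate and no division of alpha between the two primary outcomes, WOMAC pain and WOMAC function at one year.

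**The concern.** A difference in points, an SD and a standardised effect are tied by one division, so any two fix the third. Here all three are given and they disagree. The power claim rests on them, and it is the only power justification in the document.

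What is at stake is how a null result would be read. The sentence names 1.5 points as the difference to be detected, but attaches the description of clinical meaning to 0.4 SD. A reader cannot tell which of these the trial was sized for. One makes the trial larger than 80% power requires; the other makes it clearly too small. That should be settled before results are known.

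**Working it through.** **Inputs** (synopsis and section 4.6): difference 1.5 points; SD 2.65; standardised effect 0.4; two-sided alpha 0.05; 49 on physical therapy and 98 on AposTherapy; stated power 80%.

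**Step 1: is 1.5 points equal to 0.4 SD?**
- 1.5 / 2.65 = 0.566 SD.
- 0.4 × 2.65 = 1.06 points.
- The SD at which 1.5 points is 0.4 SD: 1.5 / 0.4 = 3.75.

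The synopsis prints the sentence unbroken with the same figures, so the figure break inside section 4.6 is not the cause.

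**Step 2: can the stated 80% be reproduced?** By the normal approximation, power = Φ(d × √(n₁n₂/(n₁+n₂)) − 1.96), with √(49 × 98 / 147) = 5.715.
- d = 0.566: Φ(3.235 − 1.96) = Φ(1.275) = 89.9%.
- d = 0.4: Φ(2.286 − 1.96) = Φ(0.326) = 62.8%.

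The noncentral t distribution, which is exact for a two-group comparison of means, gives the figures used below:

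| Evaluable patients | 1.5 points at SD 2.65 (d = 0.566) | 0.4 SD (d = 0.4) |
|---|---|---|
| 49:98 | 89.5% | 62.2% |
| 162 less 10%, i.e. 48.6:97.2 | 89.3% | 61.9% |

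Neither reading gives 80%. If 1.5 points and 0.4 SD are both kept and the SD is taken as 3.75, d is still 0.4 and power is again 62.2%.

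**Step 3: what does 147 detect with 80% power?** At 49:98 the detectable effect is d = 0.4935, and 0.4935 × 2.65 = 1.31 points. The document states neither figure.

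**Step 4: what would restore 80%?**
- For 1.5 points, an SD of 1.5 / 0.4935 = 3.04.
- For 0.4 SD with baseline adjustment, a baseline correlation of √(1 − (0.4/0.4935)²) = 0.59. No correlation is given, and section 5 names no covariate.
- Other settings with 147 patients also miss, for d = 0.566 and d = 0.4 respectively: 1:1 allocation gives 92.6% and 67.3%; one-sided alpha 0.05 gives 94.2% and 73.6%; two-sided alpha 0.025 gives 83.3% and 51.0%.
- Using Kruskal-Wallis lowers power for 1.5 points only to about 88% with normal data (relative efficiency 0.955), and to 84.7% at the lower bound of 0.864.

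**Step 5: numbers needed at 1:2 for 80% power (t-test).**
- d = 0.566: 38 + 76 = 114 evaluable.
- d = 0.4: 75 + 150 = 225 evaluable.

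**Minor point on the counts.** 162 × 0.9 = 145.8, about one patient short of 147, which is negligible.

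**The case against.** The arithmetic is not disputed. Four points can be made for the plan.

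1. *The error is conservative.* The text names 1.5 points as the difference to detect; at the stated SD, 80% understates the power. This stands. On that reading the trial is not underpowered and nothing in the analysis changes. The stated effect size and power are still wrong.

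2. *The 0.4 may be a stray descriptor.* The normal-approximation size for 1.5 points, SD 2.65, 80% power and 1:1 allocation is 2 × (1.96 + 0.842)² / 0.566² = 48.99, i.e. 49 per arm. That equals the planned physical therapy arm, and 98 is twice it. So 147 may be a 1:1 calculation with one arm doubled. Equally, 1.5 / (2.65 × √2) = 0.400, so 0.4 may come from the SD of a difference between two uncorrelated scores; if that SD applied to the analysis, power would be about 62%. Both origins are inference, and they point in different directions. They make the case for asking the sponsor rather than for leaving the text alone.

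3. *The SD may be the wrong figure.* This is fair: the 90% is conditional on SD 2.65. An SD of 3.75 would put power for 1.5 points itself at 62%.

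4. *One combination comes close to 80%.* Alpha 0.025 for two primary outcomes, with 147 reduced by 10% to 44:88, gives 78.7% by t-test (79.5% by normal approximation) for 1.5 points. It contradicts the stated alpha of 0.05 and the use of 147 as the number before the attrition allowance, so it does not rescue the statement.

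**Conclusion.** The statement is wrong as written and must be corrected in both places. At the stated SD, 1.5 points is 0.57 SD, not 0.4, and power at 49:98 is 89.5%, which is 9.5 percentage points above the claim. If 0.4 SD is the effect meant, power is 62.2%, nearly 18 points below the claim, and the risk of missing it is about 38%.

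These figures assume a two-group comparison of WOMAC pain means with a common SD, two-sided alpha 0.05 and no covariate adjustment, which is how sections 4.6 and 5 read. The arithmetic contradiction between 1.5, 2.65 and 0.4 needs none of these assumptions. The documents do not show which of the three figures is in error. The looseness over 147 and 162 is minor and carries no weight in this conclusion.

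**What to change.** In the synopsis and in section 4.6:

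1. State which effect is the clinically meaningful target, and confirm the SD.
2. Remove the claim that 1.5 points corresponds to 0.4 SD at SD 2.65.
3. Restate the power. If SD 2.65 is confirmed, suitable wording is: *With 147 evaluable patients (49:98) and two-sided alpha 0.05, power is about 90% for a difference of 1.5 points (0.57 SD, SD 2.65), 80% for 1.31 points (0.49 SD) and about 62% for 0.4 SD (1.06 points).* If the sponsor confirms a different SD, the figures in points should be recalculated from it.
4. If 0.4 SD is named as the target, give about 62% as its power, not 80%.
5. Minor: call 147 the evaluable number and 162 (54:108) the number randomised.

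The cost is a wording change in two places. Enrolment, data collection and analysis stay as they are. The one real consequence is that naming 0.4 SD as the target means acknowledging power of about 62%.

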4.7. Treatment protocol

Group 1: AposTherapy

AposTherapy is a biomechanical therapy that has the ability to combine the two well-established treatment strategies for knee OA: reducing loads from the affected joint by altering joint kinematics and training of the neuromuscular system by perturbation. The AposTherapy device is comprised of convex adjustable biomechanical elements ('pertupods') placed under the hind-foot and fore-foot regions of each foot. The elements are attached via a platform in the form of a shoe. This platform enables a trained physiotherapist to calibrate the biomechanical elements to a customized configuration for each patient (Figure 1).

Figure 1. The biomechanical device

The AposTherapy Device. **(a)** A biomechanical device comprising two individually calibrated elements and a foot-worn platform. The elements are attached to a platform under the hindfoot and forefoot regions. **(b)** The biomechanical elements are available in different degrees of convexity and resilience. **(c)** The specially designed sole of the platform includes two mounting rails and a positioning matrix to enable flexible positioning of each biomechanical element. [Elbaz, 2014].

During the first assessment the biomechanical device (AposTherapy device) will be individually calibrated to each patient by a physiotherapist certified in AposTherapy treatment methodology. The principle of device calibration is to achieve minimal pain while walking. For example, in knee OA with medial compartment disease, the pod-element under the hindfoot is shifted laterally from the neutral position. This shifts the center of pressure (COP) in the foot laterally, thereby reducing the magnitude of the knee adduction moment acting on the knee joint. This is done until the patient reports minimal pain during initial contact. The forefoot pod-element is shifted medially from the baseline position until the patient reports minimal pain during mid-stance to toe-off. Once the desired alignment is achieved, the patient should report immediate pain relief while walking. Following calibration patients will receive home-based exercise guidelines. During the first three weeks patients will be instructed to wear the calibrated biomechanical device for 30 minutes, while doing their daily activities (overall accumulating 10-15 minutes' walk). Patients will be instructed to gradually increase their wearing time reaching 2 hours a day following 3 months of treatment. After three months, patients will be encouraged to add outdoor walking, starting with 10 minutes and reaching 30 minutes a day. Patients will be asked to come back to follow-up meetings at the clinical center after 4 weeks, 8 weeks, 12 weeks, 24 weeks and 52 weeks. During these follow-up meetings patients will be re-assessed by the Apos therapist and, if needed, the biomechanical device will be re-calibrated.

Group 2: Traditional physiotherapy

Physical therapy for knee osteoarthritis is provided at Department of Rehabilitation Medicine, Moses Division, three times a week for 4 to 8 weeks (up to 20 sessions) depending on the progression of the subject. Each session takes about 1 hour. Physical therapist will follow the standard of care protocol available at our institution with minor adjustment as needed (Appendix 1).

Typical physical therapy regimen for knee OA includes strengthening, stretching exercise, therapeutic modality and education.

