A potential use of AposTherapy as a replacement for traditional physical therapy may yield a less costly, more effective therapy with better adherence. Problems with traditional therapy include poor patient adherence (patients often do not complete the sessions and have very poor adherence (about 50-60%) to home therapy programs [7]), added cost of travel (which may be more than \$100 per session for ambulette or access-a-ride for eligible patients), and the lack of continuation in an ongoing exercise program, leading to relapse and need for retreatment. Additionally, access to physical therapy is limited for many patients since there are not enough available outpatient therapy services to meet the needs of all patients. Finding an alternative exercise program that will increase adherence, decrease total therapy visits, and improve patient's outcomes with decreased dependence on pain medications is a high priority from both patient care and cost management perspectives.

AposTherapy potentially overcomes many of these issues with improving/modifying abnormal biomechanics (therefore decreasing pain), and a home-based exercise program utilizing footwear that causes exercise with normal activity by promoting perturbation. This biomechanical approach may significantly reduce pain and improve function in patients with

knee OA. Capitalizing on the reported excellent adherence and clinical benefit of AposTherapy in patients with significant knee OA, we propose to evaluate the biomechanical exercise (wearing an appropriately calibrated shoe at home for a prescribed amount of time each day) as a conservative treatment that may supplement or supplant traditional pain medications, interventional pain procedures and physical therapy in an at-risk urban inner city population with knee OA.

2. Study objective

The purpose of the current study is to evaluate the effect of this home-based biomechanical device and treatment (AposTherapy) in knee OA population. This will be a randomized single blinded (evaluator) trial of conventional physical therapy versus AposTherapy in patients with knee OA treated for one year.

In order to assess the efficacy of the intervention with AposTherapy on our patient population, a set of primary and secondary outcome measures will be defined:

3. Outcome measures

3.1. Primary outcome measures:

- Pain and function at 1 year following treatment initiation

3.2. Secondary outcome measure:

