4.8. Assessment time points

Visits for evaluation will be done in a blinded fashion with independent evaluators who will perform all follow-up evaluations. Patients will have all outcome measures on initial entry into the study (pre-treatment), at 4 weeks, 8 weeks, 12 weeks, 24 weeks and 52 weeks after entry into the study.

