In- /Exclusion Criteria	X							
Radiography	X							
Randomization	X							
Administer traditional physical therapy		Physical Therapy is administered according to the protocol for the duration of enrollment in the study						
Administer Biomechanical Device		X						
Adjustment Biomechanical Device			X	X	X	X		
VAS and ODI		X	X	X	X	X	X	
Secondary outcome measures		X	X	X	X	X	X	
Adverse Events		X	X	X	X	X	X	

Resources

AposTherapy	Montefiore

 • Training for Montefiore PTs • Full-time Apos resource to manage program on-site at Montefiore • AposTherapy devices 	
 • Clinical Principle Investigator Lead • Research staff – 2 coordinators • Data informatics, including patient population, demographics, historical costs, etc. • Research infrastructure including IRB, recruitment, clinical expertise • Study materials • Step counter/Fitbit monitors

Staff	Salary - Rate/Hr	Fringe	FTE or Hours	Total Cost
Attending Physician Supervision	\$165,000	30.5%	0.2	\$43,065
Study coordinator	\$0	0.0%	2	\$0
These will be Everest individuals				
Informatics costs	\$75		100	\$7,500
Biostatistical support	\$150		100	\$15,000
CMO staff support	\$65,000	30.5%	0.5	\$42,413
Total Staffing Cost				\$107,978
Materials	Cost per Unit	# of Patients	Qty	Subject Costs
Step counters:				
25% of Patients and 10% loss	\$50	37	41	\$2,050
Fitbit HR Monitors:				
25% of Patients	\$150	37	41	\$6,150
Mailing to Recover step counter/Fitbit:*	\$10	37		\$14,800

Transportation costs:	\$100	147		\$14,700
Subject Complete Reimbursement	\$100	147		\$14,700
Zeno Walkway	\$20,000		1	\$20,000
Total Materials				\$72,400
Total cost of the study				\$180,378

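### Falls are a named risk, but adverse events are scheduled only at visits, the longest gaps fall at peak device wear, and no fall outcome or analysis is planned

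*Combined protocol and SAP*

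**What the plan says.** Section 7 (Risks) lists two risks. One is muscle soreness; the other is "Minimal fall risk with use of new footwear device and exercise".

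The protocol takes falls seriously at entry. Section 4.5 excludes "Patients with more than 3 falls in the last 12 months, OR any fall with an injury in the last 12 months". After entry, falls appear only in section 7.

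The Study schedule has one row headed "Adverse Events", marked at weeks 0, 4, 8, 12, 24 and 52. Section 4.8 places the follow-up evaluations "at 4 weeks, 8 weeks, 12 weeks, 24 weeks and 52 weeks after entry into the study". No section defines an adverse event or a fall, gives a collection method, or provides a diary or contact between visits.

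Section 4.7 sets the device exposure. It starts with "During the first three weeks patients will be instructed to wear the calibrated biomechanical device for 30 minutes". Wear then rises: "Patients will be instructed to gradually increase their wearing time reaching 2 hours a day following 3 months of treatment". Next comes: "After three months, patients will be encouraged to add outdoor walking, starting with 10 minutes and reaching 30 minutes a day". The physical therapy arm attends three times a week for 4 to 8 weeks, up to 20 sessions.

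The primary outcome in 3.1 is "Pain and function at 1 year following treatment initiation". Neither 3.2 nor 4.9 lists falls or adverse events. Section 5 covers demographics and the primary and secondary outcomes only.

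**The concern.** Section 1 puts the device forward as a possible replacement for physical therapy, so a reader of the results will want to know whether it is at least as safe on the risk the protocol itself names. The plan gives that question little to work with. The visits are four weeks apart while wear is low and being built up, then 12 and 28 weeks apart once it has reached its highest instructed level and outdoor walking has been added. A fall without lasting injury, early in a 28-week interval, is easily lost if the only prompt is a visit at the end.

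Two consequences follow. Recorded falls are likely to be too few, which would make a statement of minimal risk look better supported than it is. And since the arms differ in how often participants meet staff, under-recording need not be equal between them, so a raw comparison of visit reports could be biased as well as thin. With no outcome or analysis specified, any comparison by arm would be unplanned.

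**Working it through.** The protocol states no figure for falls or adverse events, so there is none to reproduce. The sample size in 4.6 concerns WOMAC pain; only its 49:98 split is used here.

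**Visit intervals.** From weeks 0, 4, 8, 12, 24 and 52 the gaps are 4, 4, 4, 12 and 28 weeks. The last is 28/52 = 54% of follow-up and 28/40 = 70% of the time after week 12.

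**Instructed wear by interval.** Inputs are from 4.7. Assumptions: the 30 minutes is per day (the text does not say), the rise is linear from 0.5 to 2 hours a day over weeks 4 to 12 (mean 1.25), wear stays at 2 hours afterwards, and instructions are followed.

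| Period | Days × hours per day | Hours |
|---|---|---|
| Weeks 1–3 | 21 × 0.5 | 10.5 |
| Weeks 4–12 | 63 × 1.25 | 78.75 |
| Weeks 13–24 | 84 × 2 | 168 |
| Weeks 25–52 | 196 × 2 | 392 |
| Total | | 649.25 |

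- Last interval: 392/649.25 = 60%.
- Both late intervals: (168 + 392)/649.25 = 86%.

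**Sensitivity to the shape of the rise.**
- Wear held at 0.5 hours until week 12: total 602, share 392/602 = 65%.
- Wear at 2 hours from week 4: total 696.5, share 392/696.5 = 56%.
- Outdoor walking counted as an extra 0.5 hours from week 12, linear rise kept: 490/789.25 = 62%.

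**Opportunity to report.** By 4.7, therapy three times a week for 4 to 8 weeks is 12 to 24 sessions, capped at 20. Adding the five follow-up visits gives up to 25 staff contacts, against five in the device arm. The excess falls in the first 8 weeks. The Study schedule instead describes physical therapy as running throughout enrolment. The two passages should be reconciled, but on either reading the physical therapy arm meets staff more often.

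**What a comparison could show.** Faller proportions are not in the documents; these are illustrations.
- At 49:98 with 10% against 20%, the 95% half-width is 1.96 × √(0.10×0.90/49 + 0.20×0.80/98) = 11.5 percentage points, and power is 32%.
- If half the fallers are missed in each arm (5% against 10%), the difference halves to 5 points and power is 15%.
- If capture differs, the sign can mislead. With 20% fallers in both arms, full capture in one and half in the other records 20% against 0.5 × 20% = 10%.
- With no fallers among 98, the one-sided 95% upper limit is still 1 − 0.05^(1/98) = 3.0%.

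**The case against.** The strongest reply is that the plan is thinner than ideal but not blind. Adverse events are scheduled at five post-baseline visits in both arms and can be tabulated. ED visits, imaging, surgical procedures and total physician visits are a secondary outcome monitored via the CMO, which could reveal some injurious falls without relying on memory. Both points stand. A reader might infer that falls are captured only by recall, or that fall risk cannot be judged at all, but the documents support neither. No collection method is stated, so recall is an inference from a visit-only row. The utilization data remain only a partial answer: they are a cost measure, are not coded as falls, and miss falls that lead to no care.

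The risk in section 7 belongs to footwear and exercise together, and the physical therapy programme in Appendix 1 includes balance-board and uneven-surface work. That is correct, and it argues for identical capture in both arms.

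Wear hours are not fall risk. New footwear may be most hazardous early, when visits are closest together. The wear figures show where exposure lies, not where falls will occur.

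A reader might also see a conflict between the fall exclusion in 4.5 and continued wear under 4.7. There is none: 4.5 is an entry rule and says nothing about participants already enrolled. Nor can one conclude that an injury would go unnoticed for 28 weeks. The trial is single-centre with on-site staff, and the consent and contact pages are not available for review.

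**Conclusion.** The point holds in a limited form. For a risk the protocol names, it specifies no definition, collection method, outcome or analysis. Capture is scheduled only at visits, and the 12- and 28-week intervals coincide with the highest instructed exposure. About 60% of instructed wear (56% to 65% over extreme shapes of the rise, if the first 30 minutes is daily) falls in the last interval. Peak wear begins at about week 12, so that interval is the longest stretch at peak, not the only one.

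Fall counts are likely to be incomplete, possibly unequally by arm; by how much cannot be derived from the documents. The primary analysis of pain and function is unaffected. Even complete capture would give a description and not a powered comparison, so the gain is a dependable count and an honest interval.

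**What to change.** - Give both arms the same simple dated calendar recording each fall and whether it caused injury. State the definition of a fall.
- Have it returned at the existing visits to the unblinded coordinator, who already holds the randomization information under 4.3. Keep it from the blinded evaluators of 4.8. Any question about whether the device was being worn should be asked by the coordinator only, since an entry about the device would reveal the arm.
- Add falls and injurious falls to 4.9 as a descriptive safety outcome. In section 5, report by arm the number of fallers and the falls per person-year, with the difference and a 95% interval. The interval for the rate should allow for repeated falls in one person. State that the comparison is not powered.
- State how adverse events are elicited at each visit, and by whom.

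How device wear is handled after a fall is for the investigators, and nothing here proposes a rule.

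The cost is a printed sheet, a few minutes of coordinator time at visits already planned (two coordinators are in the Resources table), one table, slight participant burden and probably a higher recorded fall count. Monthly mailed returns from week 12 to week 52 would add about 9 × 147 = 1,323 contacts and are not needed: dated entries made at the time do most of the work.
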